7.7.5. Additional Analysis Specifications

Since the analyses will employ a time-to-1st event analysis for the safety endpoints, there will not be a discrete risk window; rather the time from index drug exposure to the onset of the safety endpoint will be explored. The risk will be conditional on the duration of exposure to HRT and time since last exposure.

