7. RESEARCH METHODS

7.1. Study Design

This PASS is a retrospective cohort study utilizing a healthcare claims data source (HIRD) in the US. Two (2) treatment groups (*Duavee* and E+P HRT) will be identified, followed, and reported upon using annual database updates. A new-user cohort design will be used for the main analysis and users with a history of (E+ P) HRT will be examined in sub-analyses. The study will accumulate data for 4 years (May, 2014-May, 2018) as it follows a dynamic cohort of patients that enter the study at different times, based on when *Duavee* or E+P HRT is initiated.

Figure 1 shows the length of study follow-up according to when new users enter the cohort.

The study duration was determined based on sample size calculations, and is the soonest that clinically meaningful HRs for endometrial hyperplasia and endometrial cancer can be detected. Study years and reporting intervals will run from May 1 through April 30 of the next year. Interim (follow-up) and final reports will contain both interval and cumulative data.

All patients in the HIRD who initiate *Duavee* or E+P HRT in the study period (2014-2018) will be considered for inclusion. This PASS is a retrospective cohort study using secondary data. The source data has been accruing since *Duavee* became available in the US in May, 2014. In accordance with EMA Pharmacovigilance Guidance (Module VIII)⁵, the start of a PASS using secondary data is defined to be when the analytic dataset is extracted. This will not be done for this PASS until the study protocol has been approved by the PRAC.

Follow-up will continue from the first use of *Duavee* or E+P HRT through to the earliest of the following censoring events:

- End of continuous health plan eligibility;
- Switch from *Duavee* to an E+P HRT medication or vice-versa;
- (Note: Any use of an estrogen or estrogen-containing product (Appendix 2) that differs from the HRT treatment regimen dispensed on the index date will censor follow-up. This does not include dispensing of a topical estrogen that is a single-unit

E+P HRT. As described in [Section 7.7.4](#), sensitivity analyses exploring the impact of this criterion will be performed.

- First occurrence of a safety endpoint.

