7.2.2. Exclusion Criteria

Patients meeting any of the following criteria will be excluded from the study:

- Patients with an insufficient period of enrollment prior to their index prescription (e.g., 6 or 12 months as determined prior to the start of analysis) will be excluded. This period is necessary to determine if the patient is a new initiator of *Duavee* or E+P HRT without a history of unopposed estrogen use, and also to adequately ascertain baseline covariates/patient history;
- Patients without a uterus, i.e., males, or women for whom evidence of hysterectomy is identified prior to initiation of *Duavee* or comparator E+P HRT; and
- Patients with a history of any type of cancer in their baseline period.
- Patients for whom *Duavee*, comparator E+P HRT or unopposed estrogen are identified during the baseline period will be excluded from the main analyses. They will be evaluated in separate sub-analyses.

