7.4. Time Periods

Each patient will have an index date corresponding to the date of their first prescription for *Duavee* or E+P HRT treatment after 01 May 2014. Baseline characteristics will be assessed from patient data collected prior to their index date (baseline period). A baseline period will be specified in a manner that balances inclusion of as many *Duavee* users as is feasible in the cohort with the need to ascertain covariates prior to the start of treatment. The baseline period will be determined prior to conducting analyses based on review of the distribution of prior continuous health plan enrolment among the *Duavee* cohort of patients.

As described in [Section 7.1](#), follow-up will continue from the first use of *Duavee* or E+P HRT through to the earliest occurrence of a censoring event.

[figure not shown]
Patients will accrue both person-time at risk and person-time on treatment. Analyses will consider patients at risk during the entirety of their follow-up until censoring, regardless of treatment discontinuation. Exploratory analysis will be done on the timing of events in relation to being on treatment.

Scenarios illustrating the duration of the follow-up period are presented in Figure 3.

[figure not shown]
Figure 3. Safety endpoints

- Key:**
- Enrolled in a health plan
 - Exposure to *Duavee*
 - ▨ Exposure to comparator E+P HRT

Patient A: *Duavee* cohort member censored due to use of a comparator E+P HRT

Patient B: E+P HRT cohort member censored due to end of health plan enrolment, history of MI diagnosed at baseline.

Data Source

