7.7.4. Sensitivity Analyses

Three sensitivity analyses are planned to explore the impact of censoring due to treatment switch, censoring from analyses of safety endpoints due to occurrence of any cancer type, and potential misclassification of the primary endpoints based on use of the developed algorithms.

Specifically, the main analyses for the primary and secondary endpoints will be performed including person-time after treatment switch, and the main analysis for the primary endpoints only (endometrial hyperplasia and endometrial cancer) will be performed including patients who had been censored due to cancer occurrence. The IR estimate for each primary outcome (endometrial cancer and endometrial hyperplasia) will be corrected for the PPV of the outcome algorithm as identified through validation. This will be done by multiplying the number of observed cases by the PPV point estimate, and will be presented with a 95% CI.

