- Use of administrative healthcare data for research is associated with outcome misclassification, due to missing codes or coding errors, or to limits in the time period of patient observation available in the data. This study will use well-established sources, but misclassification may still be present. Specifically, women who have had a hysterectomy before their baseline 12 month period and started either *Duavee* or E+P HRT would be misclassified as having an intact uterus. However, this misclassification would be non-differential and would not bias the study comparison.
- There may be uncontrolled residual confounding aspects due to unmeasured prescribing factors that differ between the *Duavee* and E+P HRT patient cohorts. Physicians prescribe drugs for specific medical reasons and this may introduce channeling biases whereby one cohort is at higher risk for a particular safety event. This bias could also be due to unrecorded cardiovascular and cancer risk factors such as smoking, body mass index (BMI), and family history. Because the analyses rely on automated claims collected primarily for billing purposes, some desirable data elements are not captured. Lifestyle factors such as smoking and biometric measures like BMI, for example, are systematically unavailable. Likewise, family history of endpoints is unknown. These factors present another source of residual confounding.
- Despite the large size of the HIRD, the identified safety endpoints are rare events so there will be a limit to the precision with which it can estimate elevated risks associated with *Duavee* use. Additionally, the cancer endpoints may have long latency periods from exposure and the ability to follow patients long-term will be limited by duration of enrollment in the database.

- Calculation of HRT treatment duration and time since last exposure are based upon assumptions about actual use patterns because drug dispensing is all that can be directly observed using the HIRD.
- The study size is dependent on the rate of uptake of *Duavee* in the US. The study size projections are intentionally conservative (i.e., they are lower than Pfizer marketing forecasts of uptake in the US); to allow for adequate precision even if there is limited uptake in the first year following launch. Uptake will be evaluated at the end of Year 1 and, if needed, additional data sources or extension of study duration will be discussed in the 1st Interim Report.

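### For the cancer endpoints, no planned hazard ratio leaves out early follow-up, although the protocol says these cancers may have long latency

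*Protocol*

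**What the plan says.** **Time zero.** Section 7.1: "Follow-up will continue from the first use of" either study treatment, up to the earliest censoring event.

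**Time at risk.** Section 7.4: "Analyses will consider patients at risk during the entirety of their follow-up until censoring, regardless of treatment discontinuation". Section 7.7.5 adds that "there will not be a discrete risk window". The HR comes from a Cox model for first occurrence (7.7.6.3).

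**Latency.** The limitations in 7.9 state that "the cancer endpoints may have long latency periods from exposure". No duration is given.

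**Sensitivity analyses.** Section 7.7.4: "Three sensitivity analyses are planned to explore the impact of censoring due to treatment switch", censoring at any cancer, and misclassification of the primary endpoints. None uses a lag.

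**Related provisions.**
- Section 7.2.2 excludes "Patients with a history of any type of cancer in their baseline period".
- Section 7.7.5 says "rather the time from index drug exposure to the onset of the safety endpoint will be explored", and that risk will be conditional on duration of exposure and time since last exposure.
- Section 7.4 says "Exploratory analysis will be done on the timing of events in relation to being on treatment".
- Sections 7.7.1 and 7.7.6.2 stratify incidence rates by treatment duration and time since last exposure.

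**The concern.** The protocol names latency as a limitation but specifies no HR that responds to it. The baseline exclusion removes only cancer already recorded. Disease that is present but undiagnosed at initiation stays in and counts as an event when it is first coded. A cancer coded weeks after the first fill is unlikely to have been caused by that fill.

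Two things can follow. If pre-existing disease is equally common in the two cohorts, early events add a component with HR near 1 and weaken any true later effect. If the cohorts differ in how intensively women are examined around prescribing, early events carry that difference into the HR, upward or downward. Section 7.9 itself allows for channeling between the cohorts. In a safety study either effect matters, and a reader of the cancer HRs would have no planned analysis with which to judge it.

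**Working it through.** **1. How much of the cancer information is early?** Inputs are from Table 1 (E+P, Reports 1/2/3): users 36,651 / 44,122 / 50,350; person-years 27,768 / 58,399 / 89,438; endometrial cancers 29 / 62 / 80. Section 7.5 says these come from nested pilot windows that all open on 01 January 2011 and last one, two and three years.

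- Mean follow-up = person-years / users: 27,768/36,651 = 0.76; 58,399/44,122 = 1.32; 89,438/50,350 = 1.78 years.
- In the one-year window, initiation and event both fall in the same 12 months, so all 29 cancers are first-year events. The windows are nested, so these 29 are among the 80: 29/80 = 36%. This is a minimum, because women starting in the second and third years add first-year events of their own. It takes the pilot's windows and new-user definition as described.

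**2. What could early events do to the HR?** Let f be the share of comparator events that were already present at initiation, and k the ratio at which such disease surfaces under Duavee relative to E+P. Then observed HR ≈ f·k + (1 − f)·true HR. The documents give neither f nor k, so what follows is illustration only.

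- Balanced (k = 1), true HR 1.5 (Table 1's own alternative): f = 0.10 gives 0.10 + 0.90 × 1.5 = 1.45; f = 0.25 gives 1.38; f = 0.50 gives 1.25; f = 0.75 gives 1.12.
- Unbalanced, true HR 1.0, f = 0.36: k = 0.7 gives 0.36 × 0.7 + 0.64 = 0.89; k = 2 gives 0.36 × 2 + 0.64 = 1.36.

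**3. What would a lag leave?** Start from the plan's own Report 3 interval for endometrial cancer at HR 1.0, (0.48, 2.10). Reading the Table 1 footnote literally, 5,400 × 10/12 = 4,500 Duavee person-years, gives (0.37, 2.72), which does not reproduce it. That is a separate matter, so I take the event count from the stated interval:

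- SE = ln(2.10/0.48)/(2 × 1.96) = 0.377; Duavee events = 1/(0.377² − 1/80) ≈ 7.7.

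Table 1 projects 1,800 new Duavee users per year, so even entry is a fair assumption for that cohort. With a constant event rate and no attrition, the share of person-time later than L years after index, for a study of T years, is (T − L)²/T².

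| Report | T | Left after 6 months | Left after 12 months |
|---|---|---|---|
| 1 | 1 | 25% | 0% |
| 2 | 2 | 56% | 25% |
| 3 | 3 | 69% | 44% |
| Final | 4 | 77% | 56% |

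With attrition at a rate of 0.3 per year, the Report 3 shares fall to 62% and 36%.

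- **12-month lag, Report 3:** 7.7 × 0.44 = 3.4 Duavee events, or 7.7 × 0.36 = 2.8 with attrition. At most 80 − 29 = 51 E+P events remain. With 3 and 51 events, SE = √(1/3 + 1/51) = 0.594, and the 95% CI at HR 1.0 is exp(±1.96 × 0.594) = (0.31, 3.20).
- **6-month lag, Report 3:** 7.7 × 0.69 ≈ 5.4 Duavee events. If E+P events shrink by the same factor (80 × 0.69 ≈ 56), SE = 0.452 and the CI is about (0.41, 2.42).
- **Report 1:** the stated interval (0.18, 5.60) implies about 1.4 Duavee events. None survives a 12-month lag, and 1.4 × 0.25 ≈ 0.3 survives a 6-month lag.

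**The case against.** The design is coherent without a lag: an active comparator, new users, propensity-score matching, exclusion of baseline cancer and a disclosed latency limitation. Section 7.7.7 says the aim is estimation, and a SAP, not shown, could add a lagged run. Sections 7.4 and 7.7.5 promise work on timing, and incidence rates are stratified by duration and recency of exposure. These points limit the finding but do not remove it. Start of follow-up, absence of a risk window and the list of three sensitivity analyses are all fixed in the protocol, and neither the exploratory work nor the rate strata take an early event out of any HR.

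Several stronger readings are tempting and are not supported.

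- **That the HRs are pulled toward 1 and Duavee is made to look safer.** This needs pre-existing disease to be balanced. With k between 0.7 and 2, step 2 shows movement both ways.
- **That the claims in 7.5 to rule out given HRs rest on time before harm could appear.** Those sentences concern endometrial hyperplasia; the latency statement in 7.9 concerns cancers. The protocol states no latency for hyperplasia.
- **That Table 1 shows an early excess.** It does not. E+P endometrial cancer rates per 1,000 person-years are 29/27,768 = 1.04 in the first pilot year, then 33/30,631 = 1.08 and 18/31,039 = 0.58 in the added years. These are calendar increments, so they neither prove nor exclude disease present at initiation.
- **That a particular dilution can be read off the design.** Any figure for the HR before and after some month would be invented. Even-entry shares also do not fit E+P, where 36,651 of 50,350 users (73%) enter in the first year. At no more than one first year per user, the first-12-month share for E+P is at most 44,122/58,399 = 75.6% at Report 2 and 50,350/89,438 = 56.3% at Report 3.
- **That cancer conclusions should depend on agreement between lagged and unlagged HRs.** With about 3 Duavee events left, agreement could not be judged.

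**Conclusion.** The point stands for the cancer endpoints, as a cheap improvement rather than an error that invalidates the plan. Every planned cancer HR counts from the first dispensing, the protocol acknowledges long latency, and no planned HR tests what early events contribute. The firm figures are that at least 36% of the E+P endometrial cancers projected for Report 3 are first-year events, and that mean E+P follow-up is under two years at all three interim reports. The size and direction of any bias cannot be derived from the documents, because neither the latency nor the share of disease present at initiation is given. The estimate that about 3 Duavee events remain at Report 3 after a 12-month lag assumes even Duavee entry, a constant event rate and the event count implied by Table 1.

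**What to change.** Add to Section 7.7.4, for endometrial cancer and each secondary cancer endpoint, a lagged IR and HR:

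- Start person-time 6 months after index, and 12 months after index in a second version. Both lengths are assumptions and should be labelled as such.
- Exclude women who have the event or are censored within the lag, and re-check propensity-score balance among those who remain.
- Report the result beside the main HR in each report where the threshold in 7.7.6.2 is met (at least one event in each cohort and four in total).
- State that Report 1 contains no follow-up beyond 12 months, and that cancer HRs are to be read with the lagged results and their limited precision in view.

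A lag for hyperplasia is not needed to meet this point. The cost is extra runs on data already in the analytic file; the main analysis does not change. The drawback is few events and wide intervals, roughly 0.3 to 3 at Report 3 with a 12-month lag. The 6-month version and the Final Report will be the more informative.

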7.7.6. Statistical Methods

7.7.6.1. Descriptive Analysis

Baseline characteristics and reasons for censoring will be presented for each exposure group. Counts and percentages for categorical variables, and mean, median, standard deviation and range for continuous variables will be presented. Descriptive characteristics will be presented for the following groups:

1. All new users of *Duavee* and E+P HRT included in the cohort; and
2. All new users of *Duavee* and E+P HRT with prior E+P HRT exposure.

For those study reports that include data from the NDI where the period of time captured by NDI data is different from the study period available in the automated claims (See Figure), tables showing these characteristics during the interval when NDI data are available will also be included.

7.7.6.2. Univariate/Unadjusted Analysis

As described in [Section 7.7.1](#) through [Section 7.7.2](#), IRs and their associated 95% CI overall and stratified by age, duration of treatment, time since most recent exposure and use of topical estrogen products will be presented.

For a given safety endpoint, HRs in either the univariate or multivariate analyses will not be performed until there is at least one event in both cohorts, and at least four events in total

(across cohorts). Until this threshold is reached, analyses will consist of cohort description and IR estimation.

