7.5. Study Size

The focus of the sample size calculations is to determine the precision of the estimated HR that can potentially be achieved in the study depending on estimated patient accrual, event rates, and assumed true risk. Because of the CHMP’s concerns related to endometrial safety, endometrial hyperplasia and endometrial cancer are the primary endpoints and were used for these sample size calculations.

Precision is a measure inversely related to variance in estimation. For the HRs being estimated in this study, precision is represented by the width of two-sided 95% CI.

Duavee estimates are projections based on Pfizer commercial forecasts of product uptake only; no patient data are yet available. Projections are conservative and assume a reduction of 50% from the original US market forecasts. The estimated number of E+P HRT new users, their total person-time of follow-up, and the expected number of incident endometrial safety events observed in that cohort was obtained based on pilot analyses of the HIRD from the last three years. Therefore, the most recent 3 years of E+P HRT use in the HIRD is being used to project future E+P HRT uptake and use.

In the HIRD pilot analyses, the number of new users of E+P HRT products (i.e., patients with at least 12 months of continuous eligibility prior to the first use of E+P HRT) were identified using a one-, two-, and three-year time frame: 01 January 2011 – 31 December 2011, 01 January 2011 – 31 December 2012, and 01 January 2011 – 31 December 2013. The total person-time of follow-up accrued by the E+P HRT new users was calculated during these periods of interest together with the number of endometrial cancer and endometrial hyperplasia events occurring after the start of E+P HRT use.

All estimates (Table 1) were calculated with two-sided 95% CIs. According to the study plan, there will be a 4-year accrual period and patients will be followed for at least 1 year, with the first two cohorts being followed for a longer duration.

Table 1. Estimated 95% Confidence Intervals for Hazard Ratios of Endometrial Safety

Description	First Annual Report	Second Annual Report	Third Annual Report
Estimated numbers of new users of Duavee ^a	1,800	3,600	5,400
Estimated numbers of new users of E+P HRT ^b	36,651	44,122	50,350
Estimated person-years of follow-up for E+P HRT users ^b	27,768	58,399	89,438
Estimated endometrial cancer events after the start of E+P HRT use ^b	29	62	80
HRs (95% CI)			

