Table 1. Estimated 95% Confidence Intervals for Hazard Ratios of Endometrial Safety

Description	First Annual Report	Second Annual Report	Third Annual Report
true HR=1.0	(0.18, 5.60)	(0.39, 2.56)	(0.48, 2.10)
true HR=1.5	(0.36, 6.33)	(0.68, 3.33)	(0.80, 2.83)
Estimated endometrial hyperplasia events after the start of E+P HRT use ^b	129	274	399
HRs (95% CI)			
true HR=1.0	(0.44, 2.26)	(0.64, 1.56)	(0.72, 1.39)
true HR=1.5	(0.76, 2.96)	(1.03, 2.19)	(1.13, 1.99)

a. *Duavee* estimates are projections based on Pfizer commercial forecasts of uptake only, no patient data are yet available. Person-time was calculated based on the assumption of 10 month treatment duration per patient⁹. Projections are conservative and assumed a reduction of 50% from actual US market forecasts.

b. E+P HRT users, person-time, and event estimates are derived from pilot analyses of the HIRD from the last three years of data.

Based on the projected numbers of patients initiating *Duavee* and E+P HRT as shown, for Year 1 of the US PASS, the estimated 95% CI of the HRs for the risk of endometrial hyperplasia in Table 1 imply that if the underlying (true) HR comparing *Duavee* users to E+P users is HR=1.0, then the point estimate of HR in the study will lie between 0.44 and 2.26, indicating that the study would be able to rule out the possibility that the true HR is greater than 2.26.

For Years 2 and 3, the estimated 95% CIs of the HRs for the risk of endometrial hyperplasia in Table 1 imply that if the underlying (true) HR comparing *Duavee* users to E+P users is HR=1.0, then the point estimates of HR in the study will lie between (0.64 and 1.56), and (0.72 and 1.39), respectively. This indicates that the study would be able to rule out the possibility that the true HR is greater than 1.56 at two years and 1.39 at three years.

These estimates are dependent on actual future E+P and *Duavee* drug uptake, the speed of patient accrual, safety event rates, and patient follow-up time; if these differ substantially from our estimates, then the precision of the HRs may change.

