7.7.7. Multiplicity Issues

This study will examine a number of end points, which introduces the possibility of incorrectly identifying a significant association between *Duavee* exposure and a given outcome. In order to minimize the effect of multiple endpoints, two primary endpoints, endometrial hyperplasia and endometrial cancer have been identified.

Otherwise, multiple comparisons will not be addressed in the analyses. Further, the primary purpose of this study is estimation of IRs and HRs, and not testing of hypotheses.

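### For rare endpoints, the rule that withholds HRs lets through only crude HRs above 1 and leaves a zero-event Duavee result without a comparative upper bound

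*Protocol*

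**What the plan says.** Protocol Section 7.7.6.2 sets one condition for reporting any HR, crude or adjusted, on a given safety endpoint: HRs "will not be performed until there is at least one event in both cohorts, and at least four events in total" across the two cohorts. It then adds: "Until this threshold is reached, analyses will consist of cohort description and IR estimation". Incidence rates with 95% CIs are therefore still given for each cohort, but no comparison is.

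Table 1 (Section 7.5) projects the two cohorts at very different sizes. It gives user counts and, for E+P, a row headed "Estimated person-years of follow-up for E+P HRT users". Duavee person-years are not tabulated, but footnote a states: "Person-time was calculated based on the assumption of 10 month treatment duration per patient".

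Section 7.7.7 says that "the primary purpose of this study is estimation of IRs and HRs, and not testing of hypotheses". Section 7.5 describes the expected result as the HR that the study could rule out.

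**The concern.** The rule makes publication of an estimate depend on the numerator of that estimate. When one cohort contributes nearly all the person-time, the four-event total is met mainly by that cohort. What decides whether an HR appears is then whether the small cohort has had an event. A single Duavee event in very little person-time already gives a high rate. If there is no Duavee event, the HR is left out.

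Two things are at stake in the interim reports to the EMA. The first HRs shown for rare endpoints would be a selected set lying mostly above 1. The most favourable result, no Duavee events against a number of E+P events, would come without the comparative upper bound that the study is meant to supply.

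**Working it through.** **Inputs (Table 1; reports 1 / 2 / 3).** Duavee users 1,800 / 3,600 / 5,400. E+P person-years 27,768 / 58,399 / 89,438. E+P endometrial cancer events 29 / 62 / 80. E+P hyperplasia events 129 / 274 / 399.

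**Step 1: person-time ratio from footnote a.** Duavee PY = users × 10/12 = 1,500 / 3,000 / 4,500. Ratio R = E+P PY ÷ Duavee PY = 18.5 / 19.5 / 19.9.

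**Step 2: check against the plan's own intervals.** With dE E+P events and dD = dE/R Duavee events, the interval at HR=1 is exp(±1.96·√(1/dD + 1/dE)). For hyperplasia, footnote a gives (0.47, 2.14) / (0.59, 1.71) / (0.64, 1.57). Table 1 prints (0.44, 2.26) / (0.64, 1.56) / (0.72, 1.39), so its figures are not reproduced. Solving the printed intervals for Duavee person-time gives about 1,290 / 4,440 / 8,740 PY, that is R of about 21 / 13 / 10. R is therefore not settled, and both sets are carried forward.

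**Step 3: smallest crude HR that can be reported.** Approximating the crude HR by the rate ratio, one Duavee event against k E+P events gives HR ≈ R/k. In Year 1 (R = 18.5):
- k = 3: 6.2
- k = 9: 2.1
- k = 18: 1.03
- k = 29 (endometrial cancer): 0.64

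Whenever k is below R, no crude HR under 1 can pass. That is the same as expecting fewer than one Duavee event at HR=1. With footnote-a person-time it means an E+P rate below 1/1,500, 1/3,000 and 1/4,500 per PY, or about 67 / 33 / 22 per 100,000 PY.

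**Step 4: how often this happens.** Take independent Poisson counts with mean dE for E+P and HR·dE/R for Duavee. Keep only outcomes that satisfy the rule. The protocol gives no counts for secondary endpoints, so the expected E+P counts of 5 to 19 are assumed. The row with 29 is endometrial cancer at report 1 under the rounded ratio.

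| R | Expected E+P events | True HR 1: reported / of these, above 1 | True HR 0.5: reported / of these, above 1 |
|---|---|---|---|
| 19 | 5 | 21% / 100% | 11% / 100% |
| 19 | 10 | 41% / 99.5% | 23% / 99% |
| 19 | 15 | 55% / 88% | 33% / 85% |
| 19 | 19 | 63% / 69% | 39% / 59% |
| 19 | 29 | 78% / 57% | 53% / 33% |
| 10.3 | 5 | 34% / 99% | 19% / 99% |
| 10.3 | 10 | 62% / 75% | 38% / 68% |
| 10.3 | 15 | 77% / 58% | 52% / 38% |

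Expressed as a rate, an assumed 0.2 per 1,000 PY in Year 1 (5.6 E+P and 0.3 Duavee events expected) gives an HR in 24% of cases at true HR=1. All of these are above 1, with median 3.7.

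**Step 5: the primary endpoints at true HR=1, footnote-a person-time.** Endometrial cancer in Year 1: expected Duavee events = 29/18.51 = 1.57, so P(none) = exp(−1.57) = 0.21. Of the HRs reported, 58% exceed 1. In Years 2 and 3 an HR is reported in 96% and 98% of cases, and 48% of these exceed 1 in both years. Hyperplasia in Year 1: 129/18.51 = 6.97 Duavee events expected, so an HR is reported in 99.9% of cases and 48% exceed 1.

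**Step 6: what a zero count would have shown.** For 0 Duavee against 29 E+P events, the exact conditional two-sided 95% limit uses p = 1 − 0.025^(1/29) = 0.119. The upper limit is p/(1−p) × R = 0.1356 × 18.51 = 2.5. With the Year 1 ratio implied by Table 1 (27,768/1,290 = 21.5) it is 2.9. Table 1 projects an upper limit of 5.60 for this endpoint at HR=1. Under the rule, neither 2.5 nor 2.9 would be produced.

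**The case against.** Requiring an event in each cohort has a sound reason: with none in one cohort, the Cox log HR has no finite estimate. That stands, and it justifies the condition for fitting the model. It does not justify giving no comparison at all, since an exact limit exists.

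Below the threshold both incidence rates and their CIs are still shown, so a zero count is visible. That also stands, and a reader who inferred that favourable data are suppressed would be wrong. Two separate intervals are still not a bound on their ratio.

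The single-event HRs carry very wide intervals. With R = 19, 1 against 10 events gives 1.9 (0.24 to 14.8), so few readers should take such an HR as proof of harm. Reports are cumulative (Section 10.1), so sparse early HRs are superseded.

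A reader might infer that all reported crude HRs point to harm whatever the true effect. The documents do not support that. At the projected endometrial cancer counts HRs below 1 do pass, and hyperplasia is unaffected. A broad endpoint such as all cancers covers the uterine codes, so it should not be rarer than endometrial cancer. Nor is a ratio of 19 firm. Analysed follow-up continues past discontinuation (Section 7.4), and Table 1's intervals imply a ratio near 10 by Year 3.

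Lastly, the figures are for crude HRs. Propensity score matching changes the person-time ratio. If matching were 1:1, adjusted HRs of about 1/3 could pass.

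**Conclusion.** The point holds for sparse endpoints. Where E+P events number fewer than the person-time ratio (about 10 to 21, depending on the report and on which part of Table 1 is used), every crude HR that clears the rule is above 1, including when the true HR is 0.5. A zero-event Duavee cohort never yields a comparative upper bound, and this applies to adjusted HRs too, because the same rule governs them.

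For the primary endpoints the effect is small: at the first report the endometrial cancer HR is withheld about 21% of the time at true HR=1, and hyperplasia is not affected. The bias fades once about two Duavee events are expected.

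The result rests on Poisson counts, the crude HR approximated by a rate ratio, and Table 1's projections. Section 7.9 calls the safety endpoints rare, but which secondary endpoints fall in the affected range, and at which report, is assumed. The size of the effect in the matched analysis is not established. This is a cheap improvement to reporting and does not undermine the main comparison.

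**What to change.** In Section 7.7.6.2, make comparative reporting depend on a quantity that does not turn on how events split between cohorts. Either of these would do: at least four events in total, or expected Duavee events at HR=1 (pooled rate × Duavee person-time) above a value fixed in advance. Keep one event per cohort only as the condition for fitting the Cox model.

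When the threshold is met but one cohort has no events, report the exact conditional (binomial) or profile-likelihood limit for the rate ratio in place of the HR: the upper limit if Duavee has none, the lower limit if E+P has none. State how the same principle applies to the matched analysis.

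The cost is about two sentences and a few lines of code, with no new data. The downside is a few very wide or one-sided intervals in early interim reports. While editing, reconcile Table 1's intervals with the 10-month footnote, since the two imply different person-time ratios.
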